5. STUDY DOCUMENTATION

- Study documents must be filled out completely and correctly. Ditto marks are not allowed.
- If an entry has been documented in error put a single line through the entry and initial and date the change. The Roswell Park Network QA Coordinator must be able to read what has been deleted.
- Do **NOT** use white-out, magic marker, scratch-outs.
- Do **NOT** erase entries.
- Use only black ink for documentation on the accountability form and any other study forms.
- It is the responsibility of Roswell Park to inform the Investigator/ institution as to when these documents no longer need to be retained. If, for any reason, the Investigator desires to no longer maintain the study records, they may be transferred to another institution, another investigator, or to Roswell Park upon written agreement between the Investigator and Roswell Park.

Roswell Park Protocol No.: I 35316

6. DRUG ACCOUNTABILITY

Drug accountability must be strictly maintained.

- Responsibility rests solely with the Investigator but can be delegated as appropriate (e.g., to pharmacy personnel).
- A drug accountability record form (DARF) will record quantities of study drug received, dispensed to participants and wasted, lot number, date dispensed, participant ID number and initials, quantity returned, balance remaining, manufacturer, expiration date, and the initials of the person dispensing the medication.
- Study drug supply will only be used in accordance with the IRB approved study.
- Drug accountability forms are protocol and agent specific, they are study source documents and will be used to verify compliance with the study.
- An inventory count must be performed with each transaction. Any discrepancies shall be documented and explained.
- Drug accountability forms must be stored with study related documents.
- Each medication provided for this study and each dosage form and strength must have its own DARF.
- Dispensing the wrong study supply is considered a **medication error**.
- **NEVER** replace investigational agents with commercial product.
- Do NOT “transfer”, “borrow” or “replace” supplies between studies.

7. SERIOUS ADVERSE EVENT REPORTING

The site Investigator or designated research personnel will report all SAEs, whether related or unrelated to the investigational agent(s) to the **IRB in accordance with their local institutional guidelines**. The site will notify the Roswell Park Network QA Coordinator within 1 business day of being made aware of the SAE. A preliminary written report must follow within 1 business day of the first notification using the Roswell Park SAE form:

A complete follow-up report must be sent to the Roswell Park Network QA Coordinator when new information becomes available.

8. UNANTICIPATED PROBLEM REPORTING

An unanticipated problem (UP) is any incident, experience, or outcome that meets all of the criteria in **Section 17.8**.

For all adverse events occurring that are unanticipated and related or possibly related to the research drug, biologic or intervention, the participating physician or delegated research staff from each site will notify their local **IRB in accordance with their local institutional guidelines**. The site must also notify the Roswell Park Network QA Coordinator within 1 business day of being made aware of the Unanticipated Problem by completing the **RPCI Unanticipated Problem Report Form** and faxing or emailing it to the Roswell Park Network QA Coordinator.

Appendix B ECOG/ Karnofsky Performance Scale

ECOG Performance Status Scale		Karnofsky Performance Scale	
Grade	Descriptions	Percent	Descriptions
0	Fully active, able to carry on all pre-disease performance without restriction	100	Normal, no complaints; no evidence of disease
		90	Able to carry on normal activity; minor signs or symptoms of disease
1	Restricted in physically strenuous activity but ambulatory and able to carry out work of a light or sedentary nature, e.g., light housework, office work	80	Normal activity with effort, some signs or symptoms of disease
		70	Cares for self but unable to carry on normal activity or to do active work
2	Ambulatory and capable of all self-care but unable to carry out any work activities; up and about more than 50% of waking hours	60	Requires occasional assistance but is able to care for most of personal needs
		50	Requires considerable assistance and frequent medical care
3	Capable of only limited self-care; confined to bed or chair more than 50% of waking hours	40	Disabled; requires special care and assistance
		30	Severely disabled; hospitalization is indicated although death not imminent
4	Completely disabled; cannot carry on any self-care; totally confined to bed or chair	20	Very ill; hospitalization and active supportive care necessary
		10	Moribund
5	Dead	0	Dead

Appendix C Child-Pugh Classification**Child-Pugh Classification of Severity of Liver Disease**

Modified Child-Pugh classification of severity of liver disease according to the degree of ascites, the plasma concentrations of bilirubin and albumin, the prothrombin time and, the degree of encephalopathy.

Parameter	Points assigned		
	1	2	3
Ascites	Absent	Slight	Moderate
Bilirubin, mg/dL	</= 2	2-3	>3
Albumin, g/dL	>3.5	2.8-3.5	<2.8
Prothrombin time * Seconds over control * INR	1-3 <1.8	4-6 1.8-2.3	>6 >2.3
Encephalopathy	None	Grade 1-2	Grade 3-4

A total score of 5-6 is considered grade A (well-compensated disease); 7-9 is grade B (significant functional compromise); and 10-15 is grade C (decompensated disease). These grades correlate with one- and two-year patient survival.

Grade	Points	One-year patient survival (%)	Two-year patient survival (%)
A: well-compensated disease	5-6	100	85
B: significant functional compromise	7-9	80	60
C: decompensated disease	10-15	45	35

Roswell Park Protocol No.: I 35316

Appendix D Medication Diary

Study No.: _____

Subject's Name: _____

Drug Name: _____

Cycle #: _____

Medical Record No.: _____

Study Medication Calendar for Sorafenib (Combination Therapy)

You should swallow your medication whole: without cutting, chewing, or crushing. The tablets should be taken in the morning and evening (about 1 hour before or 2 hours after eating.).

Please complete this calendar on a daily basis immediately after you take your tablets. Fill in the date for each day, write the drug dose that you take each day, and write the total number of tablets you take each day. If your dose changes; record the new dose level.

Start Date: _____

Dose: _____

Take _____ tablet(s) each time, about 12 hours apart and at least 1 hour before a meal or, 2 hours after a meal.

Cycle Day	Day 1		Day 2		Day 3		Day 4		Day 5		Day 6		Day 7									
Date																						
Time	AM	PM																				
Number of tablets taken																						
Cycle Day	Day 8		Day 9		Day 10		Day 11		Day 12		Day 13		Day 14									
Date																						
Time	AM	PM																				
Number of tablets taken																						
Cycle Day	Day 15		Day 16		Day 17		Day 18		Day 19		Day 20		Day 21									
Date																						
Time	AM	PM																				
Number of tablets taken																						
Cycle Day	Day 22		Day 23		Day 24		Day 25		Day 26		Day 27		Day 28									
Date																						
Time	AM	PM																				
Number of tablets taken																						
Cycle Day	Day 29		Day 30		Day 31																	
Date																						
Time	AM	PM	AM	PM	AM	PM																
Number of tablets taken																						

Roswell Park Protocol No.: I 35316

Please remember to bring this calendar with you to your next clinic appointment.

Note: On the day that you start your combination therapy (sorafenib + pembrolizumab) and on Day 1 of every four cycles of the combination after that, your blood will be drawn prior to receiving the intravenous pembrolizumab.

On those days (i.e. Cycle 1-Day 1, Cycle 4-Day 1, etc.), please ***do not*** take your morning dose of sorafenib until after you go to the clinic and have your blood drawn.

Coordinator's Use Only

Subject's Signature: _____

Date: _____

CRC's Signature: _____

Date: _____

Investigator's Signature :_____

Date : _____

Roswell Park Protocol No.: I 35316

Study Medication Calendar for SORAFENIB ONLY (Lead-in Phase)

Study No.: _____

Subject's Name: _____

Drug Name: _____

Medical Record No.: _____

You should swallow your medication whole: without cutting, chewing, or crushing. The tablets should be taken in the morning and evening (about 1 hour before or 2 hours after eating.).

Please complete this calendar on a daily basis immediately after you take your tablets. Fill in the date for each day, write the drug dose that you take each day, and write the total number of tablets you take each day. If your dose changes; record the new dose level.

Start Date: _____

Dose: _____

Take _____ tablet(s) each time, about 12 hours apart and at least 1 hour before a meal or, 2 hours after a meal.

Day														
Date														
Time	AM	PM												
Number of tablets taken														
Day														
Date														
Time	AM	PM												
Number of tablets taken														
Day														
Date														
Time	AM	PM												
Number of tablets taken														
Day														
Date														
Time	AM	PM												
Number of tablets taken														

* The day that you go into the clinic for your first dose of pembrolizumab is referred to as **Cycle 1-Day 1**. On the day of Cycle 1-Day, do not take your morning dose of sorafenib until **after** you have had your blood drawn at the Clinic: the blood draw will occur prior to pembrolizumab administration.

Please remember to bring this calendar with you to your next clinic appointment.

Coordinator's Use Only

Subject's Signature: _____

Date: _____

CRC's Signature: _____

Date: _____

Investigator's Signature :_____

Date : _____

Appendix E Schedule of Procedures

Trial Period	Screening	Sorafenib only	Combination (sorafenib + pembrolizumab) Treatment Cycles ³						End of Study ⁴	Post-Treatment		
			1	2	3	4	5	6 ^{3a}		Safety Follow-Up ⁵	Follow Up ⁶	Long Term Follow-Up ⁷
Phase Ib and Phase II:	Baseline¹	Day -28 to Day -1*										
Clinical Assessments												
Medical History and Pre-existing Conditions	X									X		
Prior and Concomitant Medication Review	X ⁸		X ⁹	X ⁹	X ⁹	X ⁹	X ⁹	X ⁹	X ⁹	X ⁹	X ⁹	
Physical Examination ¹⁰ ; including vital signs, body weight, & height ¹¹	X	X ²	X	X	X	X	X	X	X	X		
Child Pugh A	X											
ECOG Performance Status	X		X	X	X				X	X		
Adverse Events		X ²	X	X	X	X	X	X	X	X	X	
Survival Status			X	X	X	X	X	X		X	X	X
Laboratory Procedures												
Hematology: CBC with Differential ¹²	X	X ²	X	X	X	X	X	X	X	X		
Chemistry: CMP ¹³	X	X ²	X	X	X	X	X	X	X	X		
T3, FT4, and TSH ¹⁴	X						X		X	X		
Viral Titers: Hepatitis B and C ²² ; Hepatitis B Surface Antigen (HBsAg) and/or detectable HBV DNA and, Hepatitis C Antibody (anti-HCV)	X						X		X			

Trial Period	Screening	Sorafenib only	Combination (sorafenib + pembrolizumab) Treatment Cycles ³						End of Study ⁴	Post-Treatment		
			1	2	3	4	5	6 ^{3a}		Safety Follow-Up ⁵	Follow Up ⁶	Long Term Follow-Up ⁷
Phase Ib and Phase II:	Baseline¹	Day -28 to Day -1*	1	2	3	4	5	6 ^{3a}				
Ab), and detectable HCV RNA												
Coagulation ¹⁵	X											
Tumor Marker (AFP) ¹⁶	X			X		X			X			
Serum Pregnancy Test	X											
Imaging												
CT of chest, abdomen, and pelvis ¹⁷	X			X		X			X			
Study Drugs												
Sorafenib, po		X	X	X	X	X	X					
Pembrolizumab, IV			X	X	X	X	X	X				
Tumor Biopsies/Archival Tissue Collection/Correlative Studies Blood												
Archival Tissue Collection ¹⁸	X											
Tumor biopsy	X ¹⁸								X ¹⁹			
Correlative Studies Blood Collection ²⁰	X		X			X			X			
Pharmacokinetic Blood Sampling ²¹			X			X			X			

*The sorafenib lead in phase can extend up to Day-42 to Day-1 to allow stabilized dosing.

- 1 Within 28 days prior to start of sorafenib only study treatment (unless otherwise noted.)
- 2 Toxicity assessment within 2 weeks of starting sorafenib lead-in to include a directed physical exam and vitals.
- 3 One cycle = 3 weeks (sorafenib + pembrolizumab). Pembrolizumab to be administered on Day 1 (\pm 3 days) of each 3-week cycle. Note: After Cycle 1 Day 1, all on-study visit procedures are allowed a window of \pm 3 days unless otherwise noted. 3a The number of cycles may vary (with each patient) and additional cycles may occur, as clinically indicated. After a patient has been on pembrolizumab for more than 24 months the PI can decide if the patient can come off pembrolizumab and continue on with sorafenib treatment.

- 4 End of study or, at time decision is made to discontinue treatment (e.g. toxicity, physician decision, or patient withdraws consent).
- 5 Safety follow up to be conducted approximately 30 days (\pm 3 days) after last dose of trial treatment, or until resolution of any drug-related toxicity or before the initiation of a new anti-cancer treatment, whichever comes first.
- 6 Participants who discontinue treatment for other than disease progression will move into the follow-up phase: assessments every 3 months for 1 year or until death. Telephone contact is acceptable.
- 7 All patients will be followed by medical review every 6 months for survival.
- 8 List any medications that are ongoing, or that will be discontinued, within 1 week prior to first dose of study drug (refer to Section 10.3 for Acceptable and Prohibited concomitant medications). All concomitant medications received within 28 days before the first dose of trial treatment and 30 days after that last dose of trial treatment should be recorded.
- 9 List any ongoing medications with dose changes, as applicable. Concomitant medications administered after 30 days after the last dose of trial treatment should be recorded for SAEs and ECIs as defined in Section 17.0.
- 10 A physical exam within 1 week of consent is acceptable.
- 11 Vital signs (temperature, heart rate, respiratory rate, blood pressure), body weight and height. Height collected at baseline only.
- 12 Hematology (CBC with automated differentials): WBC, RBC, HGB, HCT, platelets, MCV, MCH, MCHC, % neutrophils, absolute neutrophils, % monocytes, absolute monocytes, % eosinophils, absolute eosinophils, % basophils, absolute basophils, % lymphocyte, absolute lymphocyte, platelet confirmation (as clinically indicated), differential confirmation (as clinically indicated). Note: Participants experiencing Grade 4 neutropenia should be monitored according to institutional guidelines. As needed at each study visit as determined by the treating physician or Investigator.
- 13 Chemistry (CMP): chloride, CO₂, potassium, sodium, BUN, glucose, calcium, creatinine, total protein, albumin, total bilirubin, alkaline phosphatase, AST, ALT, A/G ratio, BUN/creatinine ratio, osmol (Calc), anion gap.
- 14 Every 12 weeks starting from C1D1.
- 15 PT/INR and aPTT at screening and as clinically indicated.
- 16 AFP at screening and at disease assessment: six weeks after C1D1 (end of Cycle two), 12 weeks after C1D1 (end of Cycle four), every nine weeks thereafter, and at disease progression.
- 17 Imaging at Baseline, at Cycle 2 (\pm 1 week), at Cycle 4 (\pm 1 week), and then every 9 weeks (\pm 1 week).
- 18 Archival tissue collection. If available at baseline. Refer to Section 11.3.1.
- 19 Tumor biopsy: Optional at end of treatment Refer to Section 11.3.2
- 20 Prior to the start of sorafenib, at start of Cycle 1, at start of Cycle 4 and Day 1 of every subsequent 4 cycles (Cycle 8, 12, etc.), and end of study treatment. NOTE: At onset of Cycle 1, confirm that patient will actually start pembrolizumab before collecting samples. Refer to Section 11.2 for collection and processing requirements.
- 21 Pharmacokinetic samples will be collected at the start of combination treatment and processed according to Section 11.1. Patients will be advised to hold morning dose of sorafenib until after PK blood draw but before pembrolizumab.
- 22 Viral titers will be measured at baseline (and as clinically indicated in patients who have elevated baseline titers) and at every 12 weeks starting from C1D1 to assess possible effects on outcome: Hepatitis B Surface Antigen (HBsAg) and/or detectable HBV DNA and, Hepatitis C Antibody (anti-HCV Ab), and detectable HCV RNA.

Appendix F Table 1

Table 1: Dose Modification Guidelines for Non-Hepatic Pembrolizumab-Related Adverse Events

Toxicity	Hold Treatment For Grade	Timing for Restarting Treatment	Treatment Discontinuation
Diarrhea/Colitis	2-3	Toxicity resolves to Grade 0-1	Toxicity does not resolve within 12 weeks of last dose or inability to reduce corticosteroid to 10 mg or less of prednisone or equivalent per day within 12 weeks
	4	Permanently discontinue	Permanently discontinue
Type 1 diabetes mellitus (if new onset) or Hyperglycemia	T1DM or 3-4	Hold pembrolizumab for new onset Type 1 diabetes mellitus or Grade 3-4 hyperglycemia associated with evidence of beta cell failure	Resume pembrolizumab when patients are clinically and metabolically stable
Hypophysitis	2-4	Toxicity resolves to Grade 0-1. Therapy with pembrolizumab can be continued while endocrine replacement therapy is instituted	Toxicity does not resolve within 12 weeks of last dose or inability to reduce corticosteroid to 10 mg or less of prednisone or equivalent per day within 12 weeks
Hyperthyroidism	3	Toxicity resolves to Grade 0-1	Toxicity does not resolve within 12 weeks of last dose or inability to reduce corticosteroid to 10 mg or less of prednisone or equivalent per day within 12 weeks
	4	Permanently discontinue	Permanently discontinue
Hypothyroidism		Therapy with pembrolizumab can be continued while thyroid replacement therapy is instituted	Therapy with pembrolizumab can be continued while thyroid replacement therapy is instituted
Infusion Reaction	2 ^a	Toxicity resolves to Grade 0-1	Permanently discontinue if toxicity develops despite adequate premedication
	3-4	Permanently discontinue	Permanently discontinue
Pneumonitis	2	Toxicity resolves to Grade 0-1	Toxicity does not resolve within 12 weeks of last dose or inability to reduce corticosteroid to 10 mg or less of prednisone or equivalent per day within 12 weeks
		Recurrent grade 2	Permanently discontinue
Renal Failure or Nephritis	3-4	Permanently discontinue	Permanently discontinue
	2	Toxicity resolves to Grade 0-1	Toxicity does not resolve within 12 weeks of last dose or inability to reduce corticosteroid to 10 mg or less of prednisone or equivalent per day within 12 weeks
All Other Drug-Related Toxicity ^b	3 or Severe	Toxicity resolves to Grade 0-1	Toxicity does not resolve within 12 weeks of last dose or inability to reduce corticosteroid to 10 mg or less of prednisone or equivalent per day within 12 weeks
	4	Permanently discontinue	Permanently discontinue

Note: Permanently discontinue for any severe or Grade 3 drug-related AE that recurs or any life-threatening event.

^a If symptoms resolve within one hour of stopping drug infusion, the infusion may be restarted at 50% of the original infusion rate (e.g., from 100 mL/hr to 50 mL/hr). Otherwise dosing will be held until symptoms resolve and the subject should be premedicated for the next scheduled dose; Refer to Appendix G-Table 2: Infusion Treatment Guidelines, for further management details.

^b Patients with intolerable or persistent Grade 2 drug-related AE may hold study medication at physician discretion. Permanently discontinue study drug for persistent Grade 2 adverse reactions for which treatment with study drug has been held, that do not recover to Grade 0-1 within 12 weeks of the last dose.

Appendix G Table 2
Table 2: Infusion Reaction Treatment Guidelines

NCI CTCAE Grade	Treatment	Premedication at subsequent dosing
Grade 1 Mild reaction; infusion interruption not indicated; intervention not indicated	Increase monitoring of vital signs as medically indicated until the subject is deemed medically stable in the opinion of the investigator.	None
Grade 2 Requires infusion interruption but responds promptly to symptomatic treatment (e.g., antihistamines, NSAIDS, narcotics, IV fluids); prophylactic medications indicated for <=24 hrs	
Stop Infusion and monitor symptoms. Additional appropriate medical therapy may include but is not limited to:
 
 IV fluids Antihistamines NSAIDS Acetaminophen Narcotics 
Increase monitoring of vital signs as medically indicated until the subject is deemed medically stable in the opinion of the investigator.
 
If symptoms resolve within one hour of stopping drug infusion, the infusion may be restarted at 50% of the original infusion rate (e.g., from 100 mL/hr to 50 mL/hr).
 
Otherwise dosing will be held until symptoms resolve and the subject should be premedicated for the next scheduled dose.
 
Subjects who develop Grade 2 toxicity despite adequate premedication should be permanently discontinued from further trial treatment administration.
	
Subject may be premedicated 1.5h (\pm 30 minutes) prior to infusion of pembrolizumab (MK-3475) with:
 
Diphenhydramine 50 mg po (or equivalent dose of antihistamine).
 
Acetaminophen 500-1000 mg po (or equivalent dose of antipyretic).

Grades 3 or 4 Grade 3: Prolonged (i.e., not rapidly responsive to symptomatic medication and/or brief interruption of infusion); recurrence of symptoms following initial improvement; hospitalization indicated for other clinical sequelae (e.g., renal impairment, pulmonary infiltrates) Grade 4: Life-threatening; pressor or ventilatory support indicated	
Stop Infusion. Additional appropriate medical therapy may include but is not limited to:
 
 IV fluids Antihistamines NSAIDS Acetaminophen Narcotics Oxygen Pressors Corticosteroids Epinephrine 
Increase monitoring of vital signs as medically indicated until the subject is deemed medically stable in the opinion of the investigator.
 
Hospitalization may be indicated.
 
Subject is permanently discontinued from further trial treatment administration.
	No subsequent dosing
Appropriate resuscitation equipment should be available in the room and a physician readily available during the period of drug administration.		

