1.2 Secondary Objective

- To assess time to tumor progression in patients who received the combination therapy of sorafenib + pembrolizumab compared to historical data on sorafenib only treatment in patients with advanced hepatocellular carcinoma.

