4.0 Local and Study-Wide Number of Subjects

A total of 41 participants will be accrued (with a maximum of n=27 evaluable for the primary endpoint) from multiple sites, including RPCI, will be enrolled. RPCI is expected to enroll 38 participants over a period of 5 years.

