19.3 Efficacy Analysis

The response rate will be estimated as the binomial proportion of responders among evaluable patients and supported by Jeffreys' 95% confidence interval.

Time to tumor progression (TTP) will be measured from the date of study enrollment to the first observation of progressive disease. Overall survival (OS) will be measured from the date of study enrollment to the time of death from any cause. These variables will be estimated using the Kaplan-Meier method. Statistics describing the time to event distributions will be obtained from Kaplan-Meier methods and Proportional Hazards models. Continuous variables will be summarized with commonly used statistics (mean, standard deviation, median, etc.), with subgroup associations tested using the Wilcoxon Rank Sum test. Categorical variables will be summarized in contingency tables, with associations of interest assessed using Fisher's Exact Test. Given the exploratory nature of this study, all p-values less than 0.05 will be deemed statistically significant. No adjustment will be made to the significance threshold to control for the effects of multiple testing on the overall Type I error rate.

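### For patients who stop all treatment without progression, the schedule has no later imaging and no capture of progression, so TTP is by default censored at their last scan

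*Combined protocol and SAP*

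**What the plan says.** Section 19.3 defines the endpoint: "Time to tumor progression (TTP) will be measured from the date of study enrollment to the first observation of progressive disease". Section 8.0 gives the same definition. Death is not a TTP event. For the analysis of TTP and overall survival, Section 19.3 says "These variables will be estimated using the Kaplan-Meier method"; it gives no censoring rule and no sensitivity analysis for TTP. Section 1.2 sets the purpose: TTP in patients who received the combination, "compared to historical data on sorafenib only treatment in patients with advanced hepatocellular carcinoma".

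Progression is judged by irRECIST (Section 16.1, Appendix H), which rests on lesion measurement with CT preferred. In Appendix E the row "CT of chest, abdomen, and pelvis" is marked at Screening, Cycle 2, Cycle 4 and End of Study. It is blank under Safety Follow-Up, Follow Up and Long Term Follow-Up. Note 4 places the End of Study visit at the decision to discontinue. Note 6 continues: "Participants who discontinue treatment for other than disease progression will move into the follow-up phase", with "assessments every 3 months for 1 year or until death. Telephone contact is acceptable". The Follow Up column carries only concomitant medication, adverse events and survival status. Note 7 covers survival only.

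Two provisions soften this. Section 9.1 lets a patient who drops one agent for toxicity stay on study until progression. Sections 9.1 and 16.1 and note 17 also set 9-weekly imaging after Week 12 with no stated end, but none of them says that it continues after treatment stops.

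**The concern.** The patients sent to the note 6 follow-up are those whose TTP is still open when treatment ends. A site that follows the schedule takes a CT at discontinuation and then has no planned way of learning when the tumor progresses. A telephone call cannot supply an irRECIST assessment, and the follow-up column does not ask whether a scan was done elsewhere.

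Kaplan-Meier then treats these patients as having the same future risk as those still being scanned. That may not hold. Section 9.1 names toxicity and liver failure as reasons for leaving, and Appendix J ends therapy for signs of hepatic decompensation. If leavers have a higher progression hazard, the TTP curve is too favorable. The trial has no concurrent control arm in which the error could cancel, and the planned reading is against external data.

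**Working it through.** **The plan's own figure.** There is none for TTP: no sample size, event count, threshold or historical value. The only efficacy design calculation is for response rate (at least 4 of 27, 0.05 against 0.20). It reproduces, with exact alpha 0.0437 and power 0.818, but has no bearing on this point.

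**Who is affected.** Patients who stop all study treatment, have no progression on the End of Study CT, and enter the note 6 follow-up. Patients who stop one agent are not affected. The documents do not say how many patients this is.

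**Size, first model.** All inputs are assumptions:
- stayers have exponential TTP with median 5.5 months, so λ = ln 2 / 5.5 = 0.126 per month;
- a fraction p are leavers, with progression hazard kλ throughout;
- leavers exit uniformly over months 1 to 4 and are censored at exit. The share of leavers not yet exited is g(t) = 1 before month 1, (4 − t)/3 from month 1 to month 4, and 0 after.

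True curve: S(t) = (1 − p)e^(−λt) + p e^(−kλt).

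Hazard that Kaplan-Meier sees: h(t) = [(1 − p)λe^(−λt) + p kλ e^(−kλt) g(t)] / [(1 − p)e^(−λt) + p e^(−kλt) g(t)]. The estimated curve is exp(−∫h), integrated numerically.

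True median by hand for p = 0.15, k = 2: put x = e^(−λt) and solve 0.15x² + 0.85x = 0.5. This gives x = 0.537 and t = ln(1/0.537)/0.126 = 4.9 months.

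Results at k = 2, in months:

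| Leaving | KM median | True median | Difference |
|---|---|---|---|
| 5% | 5.39 | 5.30 | 0.09 |
| 10% | 5.28 | 5.11 | 0.17 |
| 15% | 5.17 | 4.93 | 0.24 |
| 34% | 4.70 | 4.29 | 0.42 |

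In the 34% row the 6-month progression-free proportion is 42.5% estimated against 38.5% true. At k = 3 and 34% the medians are about 4.1 and 3.7. At k = 1 both are 5.5 for every p: no bias.

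**Size, second model.** Here the hazard changes only at stopping. With constant hazards, 15% or 30% of patients stopping before progression, and a hazard after stopping of 1, 1.5, 2 or 3 times the on-treatment hazard, the median is overstated by 0%, 2.6% to 5.9%, 4.6% to 10.4%, and 7.6% to 17.0%. For example, with 30% stopping and ratio 2, a Kaplan-Meier median of 6.0 months corresponds to a true 5.4.

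**Against sampling error.** Simulated trials of 41 patients under the first model (34%, k = 2) give a Kaplan-Meier median with a 95% range of about 2.7 to 8 months, compared with a bias of about 0.4.

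**The case against.** **The share leaving.** Section 4.0 says "A total of 41 participants will be accrued (with a maximum of n=27 evaluable for the primary endpoint", and a reader might infer that 14 of 41, or 34%, stop without progression. The documents do not support that. The surplus covers replaced patients, and Section 9.1 includes among these the patients who do not tolerate sorafenib alone in the lead-in. They never receive the combination and lie outside the Section 1.2 population. Section 9.1 also conflicts with itself on whether patients who withdraw after starting the combination are replaced. Nor does the surplus count patients who stop after the Week 12 assessment. So 34% serves here only as an upper case.

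**Whether progression can be seen at all.** A reader might infer that it cannot be observed after treatment. That is too strong. TTP is not restricted to scheduled CT, note 6 leaves its assessments undefined, and the 9-weekly imaging has no stated end. What stands is that nothing after End of Study is scheduled and capture is unspecified. Progression already present at stopping is caught by the End of Study CT.

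**Direction.** A higher risk in leavers is a reasonable inference from the reasons for stopping, but the documents do not state it. The historical source's censoring rule is not given; if it censors in the same way, part of the bias offsets. Some patients with liver failure may die without progression, so not every censored patient hides a progression.

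**Importance.** The bias is small beside the sampling error, Section 19.3 calls the study exploratory, and the response-rate decision is not touched by this route. All of this stands and limits the severity. It does not remove the point: sampling error is reported in a confidence interval, whereas this bias would not be visible, and scan dates not collected at the time may be hard to recover.

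**Conclusion.** The point holds for patients who stop all study treatment without progression. The schedule gives them no imaging after the End of Study CT and no record of progression, and with no stated rule Kaplan-Meier censors them at the last scan. The open-ended imaging wording in Sections 9.1 and 16.1 and note 17 does not say otherwise and has to be reconciled with note 6.

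Any bias is upward if leavers progress sooner and zero if their risk is unchanged, in which case only events are lost. At a hazard ratio of 2 it is about 0.1 to 0.2 months on the median for 5% to 15% leaving, and 0.4 months in the 34% upper case. The leaving share, the exit times, the 5.5-month median and the hazard ratio are all assumed. Only TTP is affected through this route, so the severity is minor to moderate.

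**What to change.** 1. In Appendix E note 6, at each existing 3-monthly contact, record the date and result of any standard-of-care scan until progression, new anticancer therapy or death, applying irRECIST where the images allow. In the same edit, say whether the 9-weekly imaging in Sections 9.1 and 16.1 and note 17 ends with treatment.
2. In Section 19.3, state that progression found this way is a TTP event and that all other patients are censored at the last adequate tumor assessment.
3. Report how many patients stop all treatment without progression, by the reasons classified in Section 12.1. Add one sensitivity analysis that counts stopping for toxicity or investigator judgment, or death without progression, as an event. Label it as a treatment-failure type of estimand, since it answers a different question from TTP. Section 12.1 has no separate category for liver failure or clinical decline, so the analysis should use the existing categories.

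The cost is two fields on the follow-up form, a short addition to note 6, two sentences in Section 19.3 and one extra analysis. No scan is added by protocol. The downside is that routine scans are irregularly timed and may lack a formal irRECIST reading; those events should be flagged in the report.
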